3. STUDY DESIGN AND RATIONALE

3.1. Overview of Study Design

This is a randomized, double-blind, placebo-controlled, parallel-group, multicenter, Phase 1/2a study in healthy HIV-uninfected adult men and women between the ages 18 to 50 years, inclusive. A target of 150 subjects will participate in this study with 25 subjects in Group 1, 100 subjects in

^e Subjects will be divided into three groups: the first 20 enrolled subjects will have the Visit 22b 7 days post late boost, the next 20 enrolled subjects 3 days post late boost and the remainder of the subjects 14 days post late boost.

Group 2, and 25 subjects in Group 3. Group 1 represents the "base-case" regimen which allows bridging of data from this study to study VAC89220HPX2004. A diagram of the study design is provided in Table 1. Randomization will be stratified by region. Subjects will receive IM doses of study vaccine or placebo at 4 time points: Ad26.Mos4.HIV or placebo will be given at Weeks 0 and 12; Ad26.Mos4.HIV together with either Clade C gp140 plus adjuvant or a combination of Mosaic and Clade C gp140 plus adjuvant, or placebo will be given at Weeks 24 and 48.

The main study will be conducted in 3 phases: a 6-week screening period; a 48-week vaccination period during which subjects will be vaccinated at baseline (Week 0) and at Weeks 12, 24, and 48; and a follow-up period to the final main study visit at Week 72. An LTE phase (approximately 3 years after Week 72) will be performed for subjects randomized to Group 1 or Group 2, who have received all 4 vaccinations and are negative for HIV infection at Week 72. The vaccination regimens of Group 1 and Group 2 (including Ad26.Mos4.HIV and either Clade C gp140 alone or combined with Mosaic gp140) form the basis for the regimens that will likely be evaluated in future studies.

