10. SUBJECT COMPLETION/DISCONTINUATION OF STUDY TREATMENT/ WITHDRAWAL FROM THE STUDY

10.1. Completion

A subject who is not participating in the LTE phase will be considered to have completed the study if he or she has completed the assessments at Week 72.

A subject who is participating in the LTE phase will be considered to have completed the main study if he or she has completed the assessments at Week 72 and will be considered to have completed the LTE phase if he or she has completed the assessments at the last visit of the LTE phase (Week 216).

Subjects receiving the late boost vaccination will have completed the study if he or she has completed the assessments at Week 240, if opting for 12 months of follow-up post-boost, or Week 288, if opting for 24 months of follow-up post-late boost.

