## 1. INTRODUCTION

This statistical analysis plan (SAP) is applicable to all data available up to the end of the study.

The purpose of this document is to include the analyses for the late boost and the long term extension part of the study. For completeness, the description of the analyses regarding the data up to Week 72 are kept in this document but the outputs will not be repeated when data after Week 72 become available.

All the below described analyses are supposed to be performed on fully unblinded data.

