**Table 3: Phase and Period Definitions**

Phase	Phase number	Period	Period number	Interval	
				From	To
Screening	1			00:00 of the date of signing the informed consent form a	One minute prior to Dose 1 on Day 1
Regimen	2	Post-Dose 1	1	Date and time of Dose 1 (Day 1)	Minimum of: a) Maximum (28 days after first vaccination at 23:59, scheduled visit 4 weeks after first vaccination at 23:59) b) 23:59 at the date of last contact (for early discontinuation)
Follow-Up 1	3			1 minute after end of Post-Dose 1 period	Minimum of: a) One minute prior to date and time of the next vaccination b) 23:59 at the date of last contact (for early discontinuation)
Regimen	2	Post-Dose 2	2	Date and time of Dose 2 (Day 85)	Minimum of: a) Maximum (28 days after second vaccination at 23:59, scheduled visit

Phase	Phase number	Period	Period number	Interval	
				From	To
					4 weeks after second vaccination at 23:59) b) 23:59 at the date of last contact (for early discontinuation) c) One minute prior to post-dose 3
Follow-Up 2	4			1 minute after end of Post-Dose 2 period	Minimum of: a) One minute prior to date and time of the next vaccination b) 23:59 at the date of last contact (for early discontinuation)
Regimen	2	Post-Dose 3	3	Minimum of Date and Time of the two Dose 3 Injections (Day 169)	Minimum of: a) Maximum (28 days after third vaccination at 23.59, scheduled visit 4 weeks after third vaccination at 23:59) b) 23:59 at the date of last contact (for early discontinuation)
Follow-Up 3	5			1 minute after end of Post-Dose 3 period	Minimum of: a) One minute prior to date and time of the next vaccination b) 23:59 at the date of last contact (for early discontinuation)
Regimen	2	Post-Dose 4	4	Minimum of Date and Time of the two Dose 4 Injections (Day 337)	Minimum of: a) Maximum (28 days after fourth vaccination at 23.59, scheduled visit 4 weeks after fourth vaccination at 23:59) b) 23:59 at the date of last contact (for early discontinuation)
Follow-Up 4	6			1 minute after end of Post-Dose 4 period	- If late boost vaccination took place: One minute prior to late boost vaccination ((Day 1345 – Week 192) - If no late boost vaccination took place: Minimum of: a) Last available visit for completers b) 23:59 at the date of last contact (for early discontinuation)

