### 5. SAFETY

The safety and tolerability endpoints are:

- Unsolicited AEs 28 days following each vaccination
- Solicited local and systemic AEs (reactogenicity), collected daily from day of vaccination for 7 days post-vaccination (day of vaccination and the subsequent 7 days).

The safety and tolerability analysis will be performed on the FA set. Specifically, the analysis for solicited adverse events will be done on those subjects in the FA set for whom reactogenicity assessments are available in the database (either via on-site assessments or via the diary pages of the CRF).

Safety data will be tabulated per period by regimen. Only the active periods will be shown in the tables (AE, Lab, VS), except for SAEs. In addition, for a selection of tables (AE, Lab), tabulations per subject by vaccine and per dose by vaccine will be provided.

For the subject receiving the late boost vaccination, the AEs will be tabulated as follows:

- Reporting only the late boost period (post-dose 5) for the 2 LB regimens (LB Tetravalent Clade C-Mos and LB Placebo)
- Reporting all post doses (post-dose 1,2,3,4,5) for the vaccine they received (Any post-dose will not be included).

In the ‘per subject by vaccine’ analysis, the safety will be presented per periods (post-dose 1, 2, 3, 4) by vaccine rather than by regimen. A ‘post any dose’ period (= regimen phase in section 2.1) will be added, that summarizes the safety after all administered doses of a vaccine. The post-any-dose period allows determining how many subjects reported events after administration of a certain vaccine regardless the number of doses. Each subject is counted only once. In case a subject has the same event after more than one dose, it is counted only once (and in case of showing attributes, the worst corresponding attribute is shown) in the post-any dose period. The denominator is the number of subjects that received the considered vaccine in the considered period.

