### 5.1.1. Definitions

Solicited AEs shown in the tables are extracted from the diary pages of the CRF. For unsolicited AEs, only the AEs within the 28-day period following each vaccination will be presented in the safety tables except for SAE and AESI (AE of special interest), which will be captured and tabulated in the outputs covering the whole study period. All other collected unsolicited adverse events will be presented through listings.

Solicited local AEs will be by definition considered as related to the study vaccine.

The severity of the AEs will be classified as grade 1 to 4. Solicited events that are graded less than grade 1, are not considered as AE. In case no grades are available, the grading of the solicited events will occur according to the grading list in attachment 1 of the CTP.

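### End-of-study SAE and HIV-infection percentages by regimen would set placebo, which stops at Week 72, beside vaccine groups followed several times longer, because SAP Table 3 has no Week 72 cut and no person-time is planned

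*SAP*

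**What the plan says.** Who is followed, and for how long:

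- Protocol 3.1: "An LTE phase (approximately 3 years after Week 72) will be performed for subjects randomized to Group 1 or Group 2", provided they had all four vaccinations and are HIV-negative at Week 72. Placebo subjects who enter the LTE before the sponsor is unblinded are withdrawn from it (Protocol 4.4 and 9.1.9).
- Protocol 10.1: a subject outside the LTE "will be considered to have completed the study if he or she has completed the assessments at Week 72". LTE subjects complete at Week 216, and late-boost subjects at Week 240 or 288.

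How the SAP divides and reports that time:

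- SAP Table 3: Post-Dose 4 runs to 28 days after the fourth vaccination or to the "scheduled visit 4 weeks after fourth vaccination at 23:59", whichever is later (earlier for subjects who drop out). Follow-Up 4 starts one minute after that. Its end has two branches: "If late boost vaccination took place: One minute prior to late boost vaccination", and, without a late boost, "Last available visit for completers" (or last contact for early discontinuation). There is no LTE phase.
- SAP 5: "Safety data will be tabulated per period by regimen", on the Full Analysis Set. Non-active phases such as Follow-Up 4 appear in tables only for SAEs.
- SAP 5.1.1: SAEs and AESIs are "captured and tabulated in the outputs covering the whole study period".
- SAP 5.1.2 and 4.4: the statistic is the number and percentage of subjects. Exposure is a count of vaccinations and their timing.
- SAP 1: for the analyses up to Week 72, "the outputs will not be repeated when data after Week 72 become available".

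**The concern.** Protocol 2.1 makes SAEs and confirmed HIV infection over the whole study, LTE included, a primary safety endpoint. The end-of-study tables report it. In those tables a crude percentage depends on how long each subject was watched, and observation time differs between placebo and vaccine by design.

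After Week 72, LTE subjects are asked about SAEs and tested for HIV at every visit. Placebo subjects have no planned follow-up. Apart from the few placebo subjects who may briefly be in the LTE, any later event can be recorded only in a vaccine regimen.

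Follow-Up 4 also mixes two kinds of vaccine recipient in one denominator: those who left at Week 72 and those who entered the LTE, who were selected for four doses and a negative HIV test.

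At stake is an apparent vaccine-versus-placebo imbalance in SAEs or HIV infection that reflects follow-up length alone. Protocol 1.1.2.1 itself describes earlier Ad5-vector trials with more HIV-1 infections among vaccine recipients, one of them with differential loss of high-risk placebo recipients. Readers will be alert to such a pattern.

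**Working it through.** **The plan's own durations.** Protocol 3.1 gives participation of about 78, 222, 246 and 294 weeks. Six weeks of screening plus the week of the last visit gives 6 + 72 = 78, 6 + 216 = 222, 6 + 240 = 246 and 6 + 288 = 294. All four reproduce.

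**Length of Follow-Up 4** = (end day − 365) / 7. Day 365 is Week 52, four weeks after the fourth vaccination.

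- Placebo, and vaccine recipients who do not enter the LTE: (505 − 365) / 7 = 20 weeks.
- Vaccine, boosted at the nominal Day 1345: (1345 − 365) / 7 = 140 weeks. The −28/+120 day window gives 136 to 157.
- Vaccine, LTE without late boost: (1513 − 365) / 7 = 164 weeks.
- Ratios to placebo: 140 / 20 = 7.0 and 164 / 20 = 8.2.

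**Whole-study window, from first dose.** Placebo has 72 weeks. Vaccine has 216 (LTE only), 240 or 288 (late boost). Ratios: 216 / 72 = 3.0, 240 / 72 = 3.3, 288 / 72 = 4.0.

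**Expected percentage with at least one event** = 1 − exp(−rate × years), with years = weeks × 7 / 365.25. The documents give no event rate, so the rate is an assumption, set equal in all arms.

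| Window | Weeks | 0.5 per 100 person-years | 1 per 100 person-years |
|---|---|---|---|
| Follow-Up 4, placebo | 20 | 0.19% | 0.38% |
| Follow-Up 4, boosted | 140 | 1.33% | 2.65% |
| Follow-Up 4, LTE not boosted | 164 | 1.56% | 3.09% |
| Whole study, placebo | 72 | 0.69% | 1.37% |
| Whole study, LTE only | 216 | 2.05% | 4.06% |
| Whole study, late boost + 12 months | 240 | 2.27% | 4.50% |
| Whole study, late boost + 24 months | 288 | 2.72% | 5.37% |

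**Is the assumed rate plausible?** Protocol 1.1.2.2 reports no SAEs and no HIV infections in this study's Week 72 analysis. If the planned 150 subjects were all followed for 72 weeks, person-time is 150 × 72 × 7 / 365.25 = 207 person-years. With zero events, the one-sided 95% upper limit is 2.996 / 207 = 1.4 per 100 person-years, or 1.6 with 10% less person-time. A rate of 1 is therefore within that limit but towards its upper end.

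**With a cut at Week 72.** Every regimen has 20 weeks in Follow-Up 4 and 72 weeks from first dose. At 1 per 100 person-years the expected figures are 0.38% and 1.37% in all arms.

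**The case against.** The strongest reply is that the fair comparison already exists. Protocol 11.6 has a separate final main-study analysis at Week 72, with equal planned follow-up in all three arms. SAP 1 leaves those outputs standing. This holds, and it confines the problem to the later SAE and AESI tables.

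Second, the SAP never says outright that placebo appears in the end-of-study tables, and late-boost AEs have their own layout in SAP 5. This is fair, and it makes the distortion conditional. The default still points to inclusion: the safety set is everyone randomised and vaccinated, tables are by regimen, and Group 3 is one of the three regimens.

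Third, no formal safety testing is planned, listings or narratives accompany serious events as appropriate, and the protocol is open about who enters the LTE. The subjects are low-risk volunteers, unlike those in the efficacy trials described in the background. All this lowers the risk of misreading but does not make the percentages comparable.

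Two stronger readings are tempting. A reader might infer that HIV-infection percentages suffer the 20-versus-164-week contrast. They do not: SAP 5 shows non-active phases only for SAEs, and HIV infection is an AESI tabulated over the whole study, where the contrast is 3 to 4 times. A reader might also infer a large false signal by assuming a higher rate. At 5 per 100 person-years Follow-Up 4 would show 1.9% against 14.5%. But the chance of no SAE by Week 72 at that rate would be exp(−0.05 × 207), about 3 in 100,000, so the study's own result rules it out.

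**Conclusion.** The point stands for the end-of-study SAE and AESI outputs. Followed as written, the SAP would compare crude percentages over about 20 weeks for placebo with about 140, or up to 164, weeks for vaccine recipients in the Follow-Up 4 SAE column. In whole-study outputs, including HIV infection, the contrast is 72 against 216 to 288 weeks. With equal true rates of 1 per 100 person-years, the expected contrasts are about 0.4% against up to 3.1%, and 1.4% against 4.1% to 5.4%. The ratio of roughly 8 in Follow-Up 4, or 3 to 4 over the whole study, comes almost entirely from follow-up length. The absolute gap scales with the assumed rate.

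This rests on nominal visit weeks, a constant and equal rate, and tables that show all regimens. The vaccine figures are for subjects who stay to the stated week. Those outside the LTE also have about 20 weeks in Follow-Up 4, so a regimen's overall percentage would be diluted by an amount that depends on LTE uptake. It would be wrong to conclude that the trial lacks a balanced three-arm safety comparison: the Week 72 analysis provides one.

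**What to change.** - In SAP Table 3, end Follow-Up 4 at the Week 72 visit, or at last contact if earlier.
- Add an LTE phase from Week 72 to the late boost or the last LTE visit, with LTE entrants as the denominator.
- In SAP 5 and 5.1.1, limit three-regimen SAE and HIV-infection percentages to first dose through Week 72.
- Report SAEs and HIV infections in the LTE for Groups 1 and 2 only, with events per 100 person-years.
- State beside those tables that placebo has no planned follow-up after Week 72.

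The cost is SAP wording, one extra derived phase in the analysis datasets, and the matching table layouts. No new data are needed, and the Week 72 outputs are untouched.

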**NOTE:**

a The start time of screening phase is 00:00. In case an earlier date is available (e.g. for lab or vital signs then use the very first date in order to include all data)

b In case a dose is not administered, the observations end up in the previous Follow-Up phase

For the immunogenicity analyses no phases will be constructed.

The periods/phases will be used primarily for safety and concomitant medication allocation. The post-dose periods (and the regimen phase) are considered active periods/phase, the screening and follow-up phases are considered non-active phases.

For descriptive statistics over time, assessments (regardless of the investigated parameter) will be allocated to an analysis visit based on the visit number as captured in the database.

For subjects that received a first dose, but did not receive a 2nd dose while still continuing their planned visit schedule, the measurements after the planned but not administered 2nd dose will not be included in graphs and tables showing descriptive statistics over time. Those measurements will be shown in listings but it will be indicated that these are not used in the analysis. Moreover, the vaccinations done after a missed one will not be shifted to the previous one but will be considered as planned: in the example above if the 2nd is missed, the 3rd vaccination will still be reported as post-dose 3.

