² Timings of Visits 22b (Week 193), 22c (Week 196), 22d (Week 204), 23a (Week 216), 24 (week 240), and 25 (Week 288) will be determined relative to the actual day of vaccination.

³ Subjects will be divided into three groups: the first 20 enrolled subjects will have the Visit 22b 7 days post late boost, the next 20 enrolled subjects 3 days post late boost and the remainder of the subjects 14 days post late boost.

⁴ For subjects willing to participate, informed consent for the late boost vaccination and the optional 2-year post late boost follow-up visit (Visit 25) should be collected. The ICF appendix needs to be signed at the latest before any assessment is done.

⁵ Subjects not eligible for boost vaccination should continue to follow the TIME AND EVENTS SCHEDULE FOR THE LONG-TERM EXTENSION PHASE (FROM WEEK 72 ONWARDS, GROUP 1 AND GROUP 2)).

⁶ Check clinical status again before boost vaccination.

⁷ An abbreviated, symptom-directed exam will be performed as indicated by the investigator. Weight will be measured.

⁸ If the vaccination occurs on the same day as the screening, the pre dose vital signs assessment and physical examination do not need to be repeated and HIV risk assessment, contraceptive counselling, and counselling on HIV will be performed once. AE recording will occur once prior to vaccination. Post-dose assessment of vital signs and post-dose recording of AEs must still be performed.

⁹Only for female subjects of childbearing potential.

- ¹⁰ All concomitant medication should be recorded from day of vaccination until 28 days post-vaccination. At other time points, recording of concomitant medication is restricted to concomitant therapies given in conjunction with an SAE, an AESI of TTS, any chronic or recurrent use of immunomodulators/suppressors, oral or parenteral corticosteroids, any allowed vaccination and/or any HIV prevention medication, including any COVID-19 vaccination.

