Subjects enrolled in the LTE phase will be offered participation in an extension to the LTE phase to investigate the safety and immunogenicity of a late boost vaccination approximately 3 years after the last vaccination in the main study (depending on availability of IRB and HA approvals per country/site regulations). Assessment of participants' eligibility for the late boost vaccination and vaccination itself will occur within 4 weeks prior to Week 192 until 4 months after Week 192 (Visit 22a, which can be split over several visits). Eligible, consenting subjects will be randomly assigned (3:1 ratio, see Table 2 below) in a blinded fashion to active vaccination with Ad26.Mos4.HIV and bivalent gp140 (Group 1b) or placebo (0.9% saline) (Group 2b). The aim is to have at least 48 participants enrolled in the late boost extension. Randomization will be stratified by region (USA, East Africa: assuming sufficient numbers from Rwanda in the LTE phase) and by group randomized to in the main study (Group 1/Group 2). Upon receipt of the late boost vaccination, participants will be followed up for immunogenicity and safety for a further 12 months or, if they consent to longer follow-up, 24 months. Unblinded interim data analysis (sponsor unblinding only) will be performed approximately 4 weeks after the last subject received the late boost vaccination. LTE subjects declining participation or not eligible for participation in the late boost extension will complete the study at Visit 23 of the LTE phase.

The duration of the subject's participation will be approximately 78 weeks (6-week screening + 72 weeks main study) for subjects not participating in the LTE phase and approximately 222 weeks for subjects participating in the LTE phase but not receiving a late boost vaccination and approximately 246 (12-month follow-up) or 294 (24-month follow-up) weeks for subjects receiving a late boost vaccination.

After vaccination, subjects will remain under observation at the study site for at least 30 minutes for presence of any acute reactions and solicited events. In addition, subjects will record solicited events in a diary for 7 days post-vaccination as described in Section 9.1.1. See Section 12.1.3 for grading of severity of solicited AEs. From the time of local regulatory approval of protocol amendment 5 onwards, TTS is considered to be an AESI. Thrombotic events and/or

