9.1.2. Visit Windows

The maximum screening period is 6 weeks.

For the study visits, following windows will be allowed as indicated:

- Visit 3: Day 15 ± 5 days
- Visit 4: Day 29 ± 5 days
- Visit 5: Day 85 -1 week, +3 weeks (second vaccination)
- Visit 6*: Visit 5 + 14 days (Day 99) ± 5 days
- Visit 7*: Visit 5 + 28 days (Day 113) \pm 5 days
- Visit 8: Day 169 -1 week, +3 weeks (third vaccination)
- Visit 9*: Visit 8 + 7 days (Day 176) ± 1 day
- Visit 10^* : Visit 8 + 14 days (Day 183) ± 5 days
- Visit 11*: Visit 8 + 28 days (Day 197) \pm 5 days
- Visit 12: Day 253 ± 5 days
- Visit 13: Day 337 -1 week, +3 weeks (fourth vaccination)
- Visit 14*: Visit 13 + 14 days (Day 351) \pm 5 days
- Visit 15*: Visit 13 + 28 days (Day 365) \pm 5 days
- Visit 16: Day 421 ± 3 weeks
- Visit 17: Day 505 ± 3 weeks
- Visit 18 to 21 inclusive and Visit 23/Visit 23a*: Days 673 (Week 96), 841 (Week 120), 1009 (Week 144), 1177 (Week 168), and 1513 (Week 216) ± 4 weeks
- Visit 22/Visit 22a: Day 1345 (Week 192) -4 weeks/+4 months
- Visit 22b*: Visit 22a + 3, 7 or 14 days** (Day 1348 [-1/+2 days], 1352 [± 3 days] or 1359 [± 3 days]; Week 193)
- Visit 22c*: Day 1373 ± 2 weeks (Week 196)
- Visit 22d*, 24*, and 25* (optional visit): Days 1429 (Week 204), 1513 (Week 216), 1681 (Week 240) and 2017 (Week 288)

The visit window for the optional vector shedding assessments will be ± 1 day for every visit. For those vector shedding visits that are also included in the general study schedule (Visit 3 and 4), the ± 1 day window will apply instead of the general ± 5 day window listed above.

*If a subject is not vaccinated on the given day of vaccination, the timings of the visits 1, 2 and 4 weeks post-vaccination of the main study and the Visits 22b, 22c, 22d, 23a, 24, and 25 following late boost vaccination (see TIME AND EVENTS SCHEDULE) will be determined relative to the actual day of vaccination.

** Subjects will be divided into three groups: the first 20 enrolled subjects will have the Visit 22b 7 days post late boost, the next 20 enrolled subjects 3 days post late boost and the remainder of the subjects 14 days post late boost.

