9.5. Sample Collection and Handling

The actual dates and times of sample collection must be recorded in the CRF or laboratory requisition form.

See the TIME AND EVENTS SCHEDULE for the timing and frequency of all sample collections.

Instructions for the collection, handling, storage, and shipment of samples are found in the Study Procedures Manual that will be provided. Collection, handling, storage, and shipment of samples must be under the specified, and where applicable, controlled temperature conditions as indicated in the Laboratory Manual.

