## **2.4. Definition of Subgroups**

The following subgroups will be investigated for the most relevant immunogenicity assays (more details in section 6.3):

- Region (Africa, USA)
- Ad26 VNA at baseline (<LLOQ, >=LLOQ)
- Sex (Female, Male)

- Race (Caucasian, Black or African American, Asian, Othera)
- BMI [ $<18.5$ ;  $18.5-<25$ ;  $25-<30$ ;  $\geq 30$ ]

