## 6. IMMUNOGENICITY

### 6.1. Analysis specifications

The analysis of immunogenicity will be done on the PPI analysis set (Section 2.3). Data and timepoints from the subjects receiving the late boost vaccination will be reported also separated from the previous time points however the same rules defined for the main part of the study will be applied.

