#### Humoral response

For all the humoral assays the immune response values will be  $\log_{10}$ -transformed before any further handling. The  $\log_{10}$ -transformed values will be used throughout the analysis. In the graphs, original values will be displayed on the  $\log_{10}$  scale.

For each assay and at each time point geometric mean of actual values, geometric mean increases and percentage of responders, all with corresponding 95% CIs will be provided by group in the tables. Within each group, the mean fold change of Week 52 to Week 72 will be reported. The definition of responders is defined in section 6.4. for each assay. Graphical presentations will be provided displaying dots for the subject values and including the geometric mean and the percentage of responders. If available, baseline values will be summarized pooling all the groups and will be displayed on the left of each graph. Data from post-baseline timepoints will be plotted next to each other for each group, a symbol will identify the geometric mean (or the median) of each group and timepoint.

In the graphs the actual values will be shown and the LLOQ cut-off will be visualized, the values below LLOQ or below LOD will be visualized with the value imputed as described in section 6.3.

Graphs by subgroups listed in section 2.4 will be done for ELISA (Clade C C97ZA.012, Mos1) and for ADCP (Clade C C97ZA.012), Mos1).

Durability will be displayed as a line plot showing the GM/median for each vaccine regimen.

Magnitude-breadth (MB) plot for the ELISA assay will be provided at post-baseline timepoints to explore the magnitude and breadth of each individual serum sample assayed (antibody titers of 5 Clades). MB curves will show, for each possible titer threshold, the proportion of antibody titers greater than this threshold. The group-specific curve obtained as the average MB across all subjects in that group will be displayed. The AUC-MB is calculated as the average of the titers over the panel of antigens.

For BAMA the median will be reported instead of the geometric mean. Cumulative number of responses across the IgG/antigen classes will be tabulated.

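### The SAP's visit-number rule has nothing to separate the day-3, day-7 and day-14 samples that share Visit 22b, so they are pooled unless the database codes them apart

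*SAP*

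**What the plan says.** SAP 2.1 (note below Table 3) gives a single allocation rule for summaries over time: "assessments (regardless of the investigated parameter) will be allocated to an analysis visit based on the visit number as captured in the database". The same note states that no phases are built for immunogenicity, so Table 3 cannot separate samples within a visit. For late-boost data, SAP 6.1 states that "the same rules defined for the main part of the study will be applied". The humoral part of SAP 6.3 then plans the output: "For each assay and at each time point geometric mean of actual values, geometric mean increases and percentage of responders", by group.

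The protocol schedules three sampling days under one visit number and one week label. Protocol 9.1.2 lists Visit 22b as "Day 1348 [-1/+2 days], 1352 [± 3 days] or 1359 [± 3 days]; Week 193". Footnote 3 of the late-boost Time and Events Schedule assigns the days by enrolment order: "the first 20 enrolled subjects will have the Visit 22b 7 days post late boost, the next 20 enrolled subjects 3 days", and everyone after that at day 14. Protocol 2.1 has an exploratory Env-binding ELISA endpoint at 3, 7 or 14 days and at 28 days after the boost, and SAP 1.1 adopts the protocol objectives by reference.

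The SAP does not mention Visit 22b, the three cohorts or a planned-day variable. They are absent from the Late Boost Analysis Set (2.3.3), the subgroups (2.4) and the immunogenicity sections (6.1 to 6.5).

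**The concern.** In the main study one visit number means one scheduled day, so allocating by visit number works. At 22b one number covers three days in the early period after a boost, when antibody levels may be changing. A geometric mean over all 22b samples then describes none of the days the endpoint names. If the response does change between days 3 and 14, its value depends on how many subjects enrol beyond the first 40.

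A second risk concerns comparisons between subgroups. Cohort follows enrolment order. Protocol 3.1 makes late-boost participation subject to approvals: "depending on availability of IRB and HA approvals per country/site regulations". Cohort is not a randomisation stratum; Protocol 5 lists only region and main-study group. Sampling day could therefore be associated with region, site or main-study group. SAP 6.3 plans ELISA and ADCP graphs by region, and at 22b a regional difference could partly reflect sampling day. The Group 1 versus Group 2 ELISA endpoint in Protocol 2.1 names no visit, so it is touched only if it is reported at 22b.

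**Working it through.** There is no stated figure to reproduce here. The check covers the windows, the cohort sizes and an illustration under assumed kinetics.

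**Windows** (Protocol 9.1.2; vaccination = Day 1345):

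- Day-3 cohort: 1348 − 1 to 1348 + 2, which is post-boost days 2 to 5.
- Day-7 cohort: 1352 ± 3, which is days 4 to 10.
- Day-14 cohort: 1359 ± 3, which is days 11 to 17.

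Together they span days 2 to 17. The first two overlap at days 4 and 5, so a sample taken then cannot be assigned to a cohort from its date alone. Protocol 9.5 requires sample dates ("The actual dates and times of sample collection must be recorded in the CRF or laboratory requisition form"), but no passage says that cohort is recorded.

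**Cohort sizes.** The aim is at least 48 subjects, randomised 3:1 (Protocol 3.1). At N = 48 the cohorts are 20, 20 and 8: 42% at day 7, 42% at day 3 and 17% at day 14.

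**Pooled fold rise.** The fold rises are assumptions, since neither document gives any. They are for the active arm over the pre-boost level, with active subjects spread over days as the cohorts are.

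Pooled fold = 10^{[20·log10(f3) + 20·log10(f7) + (N − 40)·log10(f14)] / N}

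Example with f3, f7, f14 = 1, 2, 5 and N = 48: (20 × 0 + 20 × 0.301 + 8 × 0.699)/48 = 0.242, and 10^0.242 = 1.75. The day-14 value over the pooled value is 5/1.746 = 2.86.

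| Assumed fold at days 3/7/14 | Pooled fold, N = 48 / 60 / 70 | Day-14 ÷ pooled, N = 48 / 60 / 70 |
|---|---|---|
| 1/1/1 | 1.00 / 1.00 / 1.00 | 1.00 / 1.00 / 1.00 |
| 1/1.5/3 | 1.42 / 1.65 / 1.80 | 2.11 / 1.82 / 1.67 |
| 1/2/5 | 1.75 / 2.15 / 2.43 | 2.86 / 2.32 / 2.06 |
| 1/3/8 | 2.24 / 2.88 / 3.34 | 3.58 / 2.77 / 2.40 |

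**Day mix between subgroups.** Suppose two subgroups differ by a share x in day-14 sampling, offset entirely by day 3. Day mix alone then gives a between-subgroup ratio of (f14/f3)^x. For x = 0, 0.10, 0.25 and 0.50:

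- flat response: 1.00 throughout
- 1/1.5/3: 1.00, 1.12, 1.32, 1.73
- 1/2/5: 1.00, 1.17, 1.50, 2.24
- 1/3/8: 1.00, 1.23, 1.68, 2.83

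The documents give no late-boost enrolment by region, site or main-study group, so x is unknown and may be zero.

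**Cells after splitting** (hypergeometric, ignoring blocking). At N = 48, 8 day-14 subjects come from 36 active and 12 placebo: 6 active and 2 placebo expected, P(4 to 8 active) = 0.983, P(no placebo) = 0.080. At N = 60 the expected cell is 15 and 5, P(no placebo) = 0.0008. At N = 70 it is about 22 and 8, P(no placebo) < 0.0001.

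**The case against.** The strongest reply is that the documents show silence, not a pooled analysis. The rule defers to the database, which may hold separate codes for the three days. The endpoint SAP 1.1 imports names the days, and SAP 6.3 works time point by time point, so separate tables may be intended. All of that stands, and it is why the point is conditional. But the only operational rule written down is visit number, and the protocol supplies one number. The SAP defers assay details to the data presentation specification, not visit allocation.

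Second, recoverability. Protocol 7 requires the vaccination date and time, so the actual post-boost day is always computable; randomisation is central and an enrolment log is kept, so enrolment order should be available. That is correct and is what makes the fix feasible. It does not resolve cohort from dates at days 4 and 5.

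Third, the sizes rest on assumed kinetics, and offsetting day 14 entirely with day 3 gives the widest contrast under a rising response. Also correct: the tables show sensitivity, not an estimate.

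Fourth, splitting thins the data. If late-boost enrolment mirrored the planned 25:100 split, N = 48 would give 48 × 0.2 × 0.75 ≈ 7 active Group 1 subjects, or about 3, 3 and 1 across days 3, 7 and 14. A by-day comparison of main-study groups would say little. That limits this secondary presentation, where adjustment for day is the alternative; it does not justify an unlabelled pooled summary.

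**Conclusion.** The concern holds, at minor severity. Followed as written, with 22b held as one visit number, the SAP yields a single summary over post-boost days 2 to 17 and does not deliver the endpoint at the days it names. The text is clear on the rule and on the absence of any cohort split; how the database codes the visit cannot be seen. The loss ranges from none (flat response) to a day-14 value 3.58 times the pooled value (1/3/8-fold at N = 48), all under assumed kinetics. Confounding of day with region or main-study group is possible but not shown.

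The effect is confined to exploratory and secondary immunogenicity at this one visit, with no formal hypothesis. Active versus placebo at a pooled 22b remains a randomised comparison, of a day-averaged response. Visit 22c onward, the safety analyses and the main-study analyses are unaffected.

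**What to change.** Add to SAP 2.1 and 6.3 that Visit 22b is split into Day 3, Day 7 and Day 14 analysis visits by scheduled cohort. If the database does not hold the cohort, derive it from late-boost enrolment order rather than from sample date alone. Tabulate each day by late-boost arm with n shown. Present any region or main-study-group summary at 22b by day cohort or adjusted for it, naming the adjustment method, since SAP 6.3 currently contains no adjusted model. A day-adjusted pooled row may be added.

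The core change costs one SAP sentence and one derived visit variable, with no new samples; the cohort may have to be rebuilt from enrolment order. The price is the small day-14 cell if enrolment stops near 48, which showing n makes plain.
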